Title	A single-center pilot study of the use of hepatitis C positive donors for hepatitis C negative lung transplant recipients with post-transplant treatment of hepatitis C viremia with Mavyret
Short Title	HCV positive lung donors
Brief Summary	
Patients who are hepatitis C negative and are on the waiting list for a Lung transplant will be enrolled. Study subjects will receive a lung transplant from a deceased donor who has tested positive for hepatitis C and post-transplant surveillance for viral transmission will be performed. All patients who develop hepatitis C viremia will receive therapy with an FDA approved medication, Mavyret, for the treatment of hepatitis C. Mavyret is a pan-genotypic hepatitis C treatment with a cure rate of over 98%. All the recipients will undergo close monitoring and surveillance for the development of hepatitis C viremia post-transplant.
 
They will be monitored in order to ensure that cure of hepatitis C viremia with sustained virologic response has been achieved.

Phase	Pilot study
Objectives	
To determine safety and efficacy of the strategy of transplantation of lungs from HCV positive donors (with or without evidence of active HCV viremia). To characterize the incidence of HCV viremia in recipients whose lung donors were HCV positive. For recipients who develop viremia, to characterize the time course of the development of viremia, and subsequent clearance of viremia after treatment with Mavyret.

Methodology	Open label, single treatment arm
Endpoint	Percentage of patients with sustained virologic response after treatment for HCV after lung transplant. Incidence of viremia after receiving a lung transplant from a donor who tests positive for hepatitis C.
Study Duration	Two years
Participant Duration	One year
Duration of IP administration	Eight weeks
Population	Adult patients active on the UNOS waiting list for a lung transplant
Study Sites	Single center (NYU Langone Hospital)
Number of participants	20 patients
Description of Study Agent/Procedure	The lung transplantation will be performed per standard of care techniques, and all post-transplant management of the transplanted organ, including immunosuppression, will be carried out per standard of care. The study-specific interventions will be the treatment of all the patients with an FDA-approved drug, the surveillance for the development of hepatitis C viremia post-transplant, and then surveillance for sustained virologic response post-treatment.
Reference Therapy	Not applicable
Key Procedures	Treatment of all the patients with an FDA-approved drug, the surveillance for the development of hepatitis C viremia post-transplant, and then surveillance for sustained virologic response post-treatment.
Statistical Analysis	In this small pilot study, descriptive statistics will be used.

CONFIDENTIAL

This material is the property of the NYU School of Medicine and Langone Medical Center. Do not disclose or use except as authorized in writing by the study sponsor

Schematic of Study Design

CONFIDENTIAL

1 Key Roles

Principal Investigator

[name]
Professor of Medicine and Cardiothoracic Surgery Director, Lung Transplant Program
[name]
[name] [contact]
[contact]

Co-Investigators:

[name]
Assistant Professor of Cardiothoracic Surgery.
Surgical Director, Lung Transplantation and Mechanical Circulatory Support NYU
Langone Cardiothoracic Surgery Associates
[name]
[name] [contact]
[contact]

[name] PhD Assistant
Professor of Surgery
Vice Chair for Research, NYU Langone Transplant Institute [name],
[name]
[contact]
[contact]

[name]
Professor of Medicine
Director, Hepatology
NYU Langone Hepatology Associates [name]
[name]
[contact]
[contact]

[name], DO
Instructor, Department of Medicine
NYU Langone Pulmonary and Critical Care Associates [name]
[name]
[contact]
[contact]

Study Coordinators:

CONFIDENTIAL

Research Coordinators:

[name], MSN, ACNP-BC
Transplant Research Nurse Practitioner
NYU Langone Transplant Institute [name]
[name]
[contact]
[contact]

[name], MS, CCRC
Senior Clinical Research Coordinator
NYU Langone Transplant Institute
[name]
[name]
[contact]
[contact]

2 Introduction, Background Information and Scientific Rationale

2.1 Background Information and Relevant Literature

In New York State, 882 patients have received lung transplants since the year 2000. In that time, however 439 patients either died on the waiting list or became too sick for transplant [1]. Thus, for every 2 patients waitlisted in New York, one patient will die or become too sick for transplant before an organ becomes available. The shortage of organs available for lung transplantation directly results in loss of life.

At the same time, since 2000, in New York alone, thousands of donor organs available for transplantation were discarded because of donor history of HCV infection or exposure [2]. With the availability of new and well-tolerated direct-acting antiviral agents, cure rates for chronic HCV infection approach 100% [3]. Treatment of HCV naïve transplant recipients who develop donor-derived HCV infection post-transplant would be expected to be equally successful. Thus, if post-transplant antiviral treatment could enable HCV positive lung donors to be utilized for negative recipients, then the current donor pool has the potential to eliminate waitlist mortality.

There is, in fact, precedent for this as a viable strategy to narrow the gap between organ supply and demand. A recently study in which HCV positive donor kidneys were transplanted into HCV negative recipients demonstrated both excellent outcomes in terms of allograft function, and 100% HCV cure rates among the recipients [4]. Other ongoing and unpublished series of kidney transplant recipients [5] and of heart transplant recipients [6] have observed that only about 70% of HCV negative recipients who receive an organ from a HCV positive donor actually develop HCV viremia post-transplant. This is not surprising since the designation for HCV donor positivity by UNOS is a positive test for *either* anti-HCV antibody *or* HCV RNA. Donors who test positive for HCV antibody alone may have a falsely positive test, or may have had a prior exposure to HCV with subsequent virus clearance; in either scenario, there would be no risk of transmission of HCV infection to a recipient. It is estimated that one-third of donors designated as HCV positive is, in fact, non-viremic [7].

In this pilot study, we propose utilizing HCV positive donors for HCV negative patients on the waiting list for a lung transplant at NYU Langone. Following transplant we will perform serial surveillance for the transmission of HCV viremia from donor to recipient. **We will start HCV therapy post-transplant once viremia is detected. The rationale for delaying treatment until viremia is detected is to prevent unnecessary treatment in patients who never develop viremia.** The main objective is to determine the safety and efficacy of the strategy of transplantation of lungs from HCV positive donors (with or without evidence of active HCV viremia). To evaluate this clinical objective, we will characterize the incidence of HCV viremia in recipients whose lung donors were HCV positive and for recipients who develop viremia, to characterize the time course of the development of viremia, and subsequent clearance of viremia after

CONFIDENTIAL

CONFIDENTIAL

This material is the property of the NYU School of Medicine and Langone Medical Center. Do not disclose or use except as authorized in writing by the study sponsor
Interventional Template Version: 28 APR 2017

With the exception of the use of HCV therapy and the blood testing to evaluate the viremia and the response to therapy, all the other aspects of management of the lung transplant recipients will follow standard of care practices and protocols for lung transplant recipients at NYU Langone Health.

Willingness to participate in this trial will afford patients quicker access to lung transplantation, and will have the potential to reduce if not eliminate waitlist mortality. In particular, the availability of lungs for transplantation in New York State is among the lowest in the country and the evaluation of HCV donors will increase the opportunities for our waitlisted patients to receive organ offers.

2.2 Name and Description of the Investigational Agent

Mavyret (glecaprevir/pibrentasvir)
Manufacturer: AbbVie, Inc., North Chicago IL

Mavyret is an FDA-approved, marketed drug clinically indicated for the treatment of HCV infection in patients without cirrhosis.

Its formulation is as an oral tablet containing two antiviral agents: glecaprevir and pibrentasvir. Glecaprevir is an inhibitor of the HCV NS3/4A protease, which is essential for viral replication. Pibrentasvir is an inhibitor of the HCV NS5 protease, which is necessary for RNA replication and virion assembly. Mavyret is active against all known strains of HCV.

2.2.1 Preclinical Data

In vitro studies demonstrating efficacy of glecaprevir and pibrentasvir at preventing replication of all strains of HCV were published prior to the initiation of clinical trials for these agents. In vitro the two agents act synergistically and have high potency with low rates of resistance. [8]

2.2.2 Clinical Data to Date

In Phase 3 clinical trials, 8 weeks of Mavyret therapy achieved high rates (98%) of SVR across all genotypes (1-6) of HCV in patients with HCV infection without cirrhosis. Clinical trials involved over 2300 patients in 27 countries. Based on the results of clinical trials, the FDA approved Mavyret for use in the treatment of HCV (all strains) in patients without cirrhosis. (ClinicalTrials.gov identifiers: NCT02651194, NCT02642432, NCT02640482, NCT02636595, NCT02604017, NCT02446717, NCT02640157, NCT02243293). [9-14]

Included in the clinical trial populations were patients with severe renal impairment (stage 4 or 5 CKD). In this population, Mavyret was found to be effective in achieving a high rate of SVR and no dosing adjustment was required. [15]

2.2.3 Dose Rationale (if applicable)

The dose used will be the standard dosing regimen for its FDA approved indication, three tablets taken once daily with food (total daily dose: glecaprevir 300mg and pibrentasvir 120mg)

2.3 Rationale

There is a vast shortage of available organs for lifesaving lung transplants. Donors with history of HCV represent an unutilized source of organs that could potentially eliminate the current waiting list mortality. With the emergence of new, FDA approved treatments, HCV disease is now curable in nearly 100% of patients who contract it. By transplanting patients with HCV-positive donor lungs, this study will offer the benefit of avoiding waiting list mortality, followed by treatment (with the expectation of cure) of HCV in the event of transmission.

CONFIDENTIAL

2.4 Potential Risks & Benefits

2.4.1 Known Potential Risks

Risks of treatment failure: HCV mutation can lead to drug resistance and treatment failure. In patients administered Mavyret, the risk of this was 2% or less. For patients with treatment resistant HCV, rescue therapy with alternative agents can result in cure of up to 100% depending upon the genotype. Guidelines for the treatment of resistant HCV strains are published and updated regularly. [16]

Risks of treatment intolerance: Over multiple clinical trials. The overall rate of medication related adverse events leading to permanent discontinuation prior to completion of an 8-week course of therapy was 0.1% [17].

Risk of acute hepatitis C infection: Acute hepatitis C is asymptomatic in 66-75% of patients. The risks of acute HCV leading to fulminant hepatic failure are believed to be very low, however case reports of this do exist [18]. To minimize this already very low risk, we are starting treatment in all the patients at the time of transplant before any viremia is even detected.

Risk of chronic hepatitis C infection: Patients who prove refractory to all therapy including rescue therapy and develop persistent viremia are at risk to develop chronic HCV infection, which has the potential to cause cirrhosis/end-stage liver disease, the potential for the need for liver transplantation and/or death. We expect our treatment failure rate in this study to be 0%, therefore we expect the risk of chronic HCV infection to be 0%. In the event of a treatment failure, the risks of developing chronic HCV must be considered. It is estimated that approximately 15-30% of patients with chronic HCV develop cirrhosis/end-stage liver disease over 20-30 years. [19]. This risk should be compared to the risk of death on the lung transplant waiting list. The reported one-year mortality for a waitlisted patient without a transplant is as high 26.7% [20].

The efficacy of HCV treatment with Mavyret is high (98%). The efficacy of rescue therapies approaches 100%. Even in the event of a treatment failure, the risk of cirrhosis and liver disease secondary to chronic HCV are low. We believe that the survival benefit of receiving an earlier lung transplant, by accepting an organ from a HCV-positive donor, far outweighs the risks of HCV exposure and possible treatment failure.

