10.5 Sample Size

20 patients are expected to enroll in this trial.

We expect that less approximately 70% of patients will develop evidence of HCV infection transmitted from the HCV-positive donor and will be treated for HCV infection. We expect that 100% of the patients who are treated for HCV viremia will achieve SVR.

This is a single-arm study with no comparison group. The power to detect a difference in observed versus expected depends upon the true efficacy of the therapy. The reported efficacy of the therapy is 98%.

With an estimated 7 patients who will be treated, a single treatment failure will be regarded as a significant deviation from the expected outcome.

CONFIDENTIAL

11 Source Documents and Access to Source Data/Documents

Source data is all information, original records of clinical findings, observations, or other activities in a clinical trial necessary for the reconstruction and evaluation of the trial. Source data are contained in source documents. Examples of these original documents, and data records include: hospital records, clinical and office charts, laboratory notes, memoranda, subjects' diaries or evaluation checklists, pharmacy dispensing records, recorded data from automated instruments, copies or transcriptions certified after verification as being accurate and complete, microfiches, photographic negatives, microfilm or magnetic media, x-rays, subject files, and records kept at the pharmacy, at the laboratories, and at medico-technical departments involved in the clinical trial. It is acceptable to use CRFs as source documents.

If this is the case, it should be stated in this section what data will be collected on CRFs and what data will be collected from other sources.

The study case report form (CRF) is the primary data collection instrument for the study. All data requested on the CRF must be recorded. All missing data must be explained. If a space on the CRF is left blank because the procedure was not done or the question was not asked, write "N/D". If the item is not applicable to the individual case, write "N/A". All entries should be printed legibly in black ink. If any entry error has been made, to correct such an error, draw a single straight line through the incorrect entry and enter the correct data above it. All such changes must be initialed and dated. **DO NOT ERASE OR WHITE OUT ERRORS.** For clarification of illegible or uncertain entries, print the clarification above the item, then initial and date it.

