- Pregnant Partner Contact Card
- Sample Willingness to Participate Form
- Sample Fact Sheet
- SOP for specimen handling
- Accreditation for the Transplant Laboratory
- Specimen collection and shipping instructions for Quest Laboratories

CONFIDENTIAL

19 Schedule of Events: Surveillance post-transplant with an 8 weeks MAVYRET treatment phase included

Activity	Screening visit (POD-365 to -1)	SURVEILLANCE PHASE					
		POD0	POW1 (+/- 2 day)	POW2 (+/- 3 days)	POW3 (+/- 3 days)	POW4 (+/- 5 days)	POW5 (+/- 5 days)
Study team procedures							
Acknowledgement of willingness to participate and provision of fact sheet	X						
Medical History		X					
Physical Exam		X					
Height		X					
Weight		X					
Vitals signs		X					
Review all donor and recipient inclusion/exclusion criteria		X					
Signing of informed consent		X					
Study specific interventions							
Lung transplant operation		X					
Mavyret treatment (Start and follow up)		X ¹					
Study specific laboratory tests							
Donor serum HCV genotyping		X					
Recipient serum HCV genotyping		Any time during the study (x1) once there is documentation of positive HCV RNA Quantitative (PCR)					
HCV RNA Quantitative (PCR)	X	X ²	X	X	X	X	X
HCV serology (HCV Ab)	X	X ²	X	X	X	X	X

X¹ Mavyret will be initiated post lung transplantation once a viral load is detected

X² If screening lab(s) specifically HCV RNA Quantitative (PCR) and HCV serology (HCV Ab) are performed 14 days or less prior to POD 0, those labs will not be repeated at the POD 0 timepoint.

CONFIDENTIAL

This material is the property of the NYU School of Medicine and Langone Medical Center. Do not disclose or use except as authorized in writing by the study sponsor
Interventional Template Version: 28 APR 2017

Activity	SURVEILLANCE PHASE			POW9 (+/- 5 days)	POW10 (+/- 5 days)	POW11 (+/- 5 days)
	POW6 (+/- 5 days)	POW7 (+/- 5 days)	POW8 (+/- 5 days)			
Study team procedures						
Study specific interventions						
Mavyret treatment (Start and follow up)	X ¹					
Study specific laboratory tests						
Recipient serum HCV genotyping	Any time during the study (x1) once there is documentation of positive HCV RNA Quantitative (PCR)					
HCV RNA Quantitative (PCR)	X	X	X	X	X	X
HCV serology (HCV Ab)	X	X	X	X	X	X

Activity	POW12 (+/- 5 days)	POW 24 - Interim assessment visit (+/- 14 days)	POW 52 - Final assessment visit (+/- 14 days)
Study team procedures			
Mavyret treatment (Start and follow up)	X ¹		
Medical History			X
Physical Exam			X
Height			X
Weight			X

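### The risk section credits treatment of every patient at transplant, before viremia, as the protection against fulminant hepatic failure, but section 2.1 and the schedule start Mavyret only on detected viremia

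*Combined protocol and SAP*

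**What the plan says.** Three places state when Mavyret starts.

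- Section 2.4.1, in the paragraph on acute hepatitis C, acknowledges case reports of fulminant hepatic failure, calls the risk very low, and gives as its mitigation: "we are starting treatment in all the patients at the time of transplant before any viremia is even detected".
- Section 2.1 states: "We will start HCV therapy post-transplant once viremia is detected". It also gives the reason: "The rationale for delaying treatment until viremia is detected is to prevent unnecessary treatment in patients who never develop viremia".
- Footnote X1 to the Schedule of Events states: "Mavyret will be initiated post lung transplantation once a viral load is detected".

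Other places say who is treated without giving a start time. The Brief Summary has "All patients who develop hepatitis C viremia will receive therapy with an FDA approved medication, Mavyret". Section 2.3 describes transplantation "followed by treatment (with the expectation of cure) of HCV in the event of transmission". Section 10.2 frames the hypothesis around patients who develop viremia, and section 10.5 expects that "less approximately 70% of patients will develop evidence of HCV infection transmitted from the HCV-positive donor and will be treated for HCV infection".

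Some text leans the other way. Two Protocol Summary rows (Description of Study Agent/Procedure and Key Procedures) list treatment of all patients as a study intervention. Section 6.1 defends the use of Mavyret when no viremia is evident at transplant. Section 5.5 describes at least 12 months of participation, of which 10 months follow therapy.

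**The concern.** Section 2.4.1 is where the protocol weighs HCV exposure against death on the waiting list. Its sentence on early treatment is the only specific mitigation it offers for acute HCV. If treatment really waits for a positive PCR, that weighing credits a protection that participants do not receive.

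The two rules also lead to different conduct. A clinician following 2.4.1 would dose everyone at transplant; one following 2.1 and the schedule would wait. The choice matters for the results too. Section 3.2 and sections 10.4.1 and 10.4.3 describe the incidence of viremia after transplant and the time to its appearance. Dosing everyone before viremia could change both quantities.

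**Working it through.** The check is mainly a comparison of text, with two short calculations.

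**1. Start rule.** Section 2.4.1: all patients, at transplant, before viremia. Section 2.1: after detection, as a deliberate delay with a stated reason. Schedule footnote X1: after detection. The first cannot hold together with the other two, and nothing in the available text reconciles them. The visit-by-visit text of section 7.3 is listed in the contents but was not in the text available for this review.

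**2. Which rule is operative.** The trigger is explicit in 2.1 and in the schedule. It fits the Brief Summary, 2.3, 10.2, 10.5 and the viremia-incidence endpoint. Treatment at transplant is explicit only in 2.4.1. The two Summary rows and 6.1 are compatible with it but give no start time.

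**3. What the design delivers.** The schedule places HCV RNA tests weekly from POW1 to POW12, then at POW24 and POW52, with Mavyret on detection. Section 7.2.1 adds review of standard-of-care ALT, AST and bilirubin. Section 8.5 halts enrollment after an SAE related to acute HCV, but that acts only after an event. None of these is treatment before viremia.

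**4. Number treated.** Inputs from section 10.5: 20 enrolled, about 70% infected and treated, and a stated count in "With an estimated 7 patients who will be treated".

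- Literal 2.4.1: 20 of 20.
- Trigger at 70%: 20 × 0.70 = 14.
- The stated 7 is not reproduced: 7 / 20 = 35%. This mismatch within 10.5 is a separate matter.

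Under either figure, the trigger treats fewer than all patients.

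**5. What section 5.5 implies.** Its own figures give 12 − 10 = 2 months for everything before post-therapy follow-up, and sections 6.1.5 and 6.1.8 set an 8-week course. For a start at week w and a final visit at POW52, post-therapy follow-up is 52 − w − 8 = 44 − w weeks. Using 365.25 / 12 = 30.44 days per month:

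| Start (weeks after transplant) | Follow-up (weeks) | Months |
|---|---|---|
| 0 | 44 | 308 / 30.44 = 10.1 |
| 1 | 43 | 301 / 30.44 = 9.9 |
| 4 | 40 | 280 / 30.44 = 9.2 |
| 12 | 32 | 224 / 30.44 = 7.4 |

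Ten months therefore fits therapy that starts at transplant or within about a week of it. Later detection gives less follow-up by POW52, and a patient who never becomes viremic has no post-therapy period. Section 5.5 states no start rule, but its arithmetic matches 2.4.1 better than a trigger with an open start date.

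**The case against.** The strongest reply is that this is one wrong sentence about a risk the protocol already calls very low, and that real protection exists. Weekly HCV RNA testing with treatment on detection is an active safeguard, supported by liver tests, the halting rule and a hepatologist on the DSMB. That stands, and it limits the weight of the point. A reader might infer from the contradiction that patients are left unprotected against acute HCV; the documents do not support that.

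A second reply is that preferring the trigger is a judgement, since 2.4.1, the two Summary rows, 6.1 and 5.5 all lean towards early or universal treatment and the text of 7.3 is missing. This stands in part. The contradiction itself is certain. The preference for the trigger rests on its explicit statement and rationale in 2.1, its place in the schedule and its fit with the endpoints.

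Three stronger readings are tempting. One is that delaying treatment is a design error; the protocol gives a reason for the delay, and nothing in it shows the delay to be unsafe. Another is that participants are misinformed. Section 13.3.1 says consent forms describe the risks, but the form was not supplied and nothing shows that it repeats the sentence. The third is to treat the number never dosed, or the intervals between scheduled PCR tests, as a measure of risk. The plan gives no expected time to viremia, so those figures describe the schedule only.

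**Conclusion.** The point holds as an internal inconsistency in the treatment-start rule and should be fixed. The mitigation credited in 2.4.1 is not the one set by 2.1 and the schedule. The contradiction is more than clerical, because the texts give opposite start rules for the study drug and the risk assessment relies on the wrong one.

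Its size is a matter of text: one false mitigation statement, with two Summary rows, 6.1 and 5.5 to be aligned. The calculations show only that the rules differ in who is treated and when. No harm rate can be derived, and no change to the SVR analysis or the sample size is shown to follow.

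The conclusion assumes that the viremia trigger is the intended rule, which the sponsor should confirm. If section 7.3 repeats the trigger, 2.4.1 is still wrong; if it calls for treatment at transplant, the conflict is wider.

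**What to change.** Keep the viremia-triggered rule and align the text to it.

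1. **Section 2.4.1.** Replace the sentence with the mitigation in use: HCV RNA is tested weekly from POW1 to POW12 and at POW24 and POW52, Mavyret starts on the first positive PCR, and standard-of-care liver tests are reviewed.
2. **Protocol Summary.** In the Description of Study Agent/Procedure and Key Procedures rows, limit treatment to patients who develop HCV viremia.
3. **Section 6.1.** Rewrite the paragraph that justifies use without viremia at transplant. Adding one sentence would leave the paragraph arguing against itself, because it supports the position that use is within the approved indication.
4. **Section 5.5.** State that post-therapy follow-up depends on the treatment start date, and that patients who never become viremic are followed for 12 months from transplant.
5. **Consent form and fact sheet.** Confirm that both state the same rule, and correct them if they do not.

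The cost is a text amendment with IRB approval under section 13.2. No visits, tests or patients are added.

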10.4.2 Analysis of the Primary Efficacy Endpoint(s)

The primary endpoint will be percentage of patients with sustained virologic response after treatment for HCV after lung transplant.

We expect that 100% of patients who are treated will achieve SVR. SVR will be defined as the absence of detectable HCV RNA Quantitative (PCR) testing 3 months after the completion of the treatment course. Any failure of therapy will be considered significant and will result in the halting of further enrollment until further discussed by the safety monitors and the IRB.

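### Section 2.4.1 gives the expected treatment-failure rate as 0%, against the 2% or less reported in the same section, and so states a 0% risk of chronic HCV with more certainty than the plan supports

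*Combined protocol and SAP*

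**What the plan says.** Section 2.4.1 (Known Potential Risks) takes up treatment failure first. It refers to viral resistance leading to failure and says "In patients administered Mavyret, the risk of this was 2% or less". On what follows a failure, it says "rescue therapy with alternative agents can result in cure of up to 100% depending upon the genotype".

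Under the risk of chronic infection it sets the condition: "Patients who prove refractory to all therapy including rescue therapy and develop persistent viremia are at risk to develop chronic HCV infection". It then states: "We expect our treatment failure rate in this study to be 0%, therefore we expect the risk of chronic HCV infection to be 0"%. The closing paragraph of the section gives Mavyret's efficacy as 98% and adds "The efficacy of rescue therapies approaches 100"%.

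Elsewhere, Section 2.2.2 reports 98% SVR in the Phase 3 trials, and Section 10.5 says "The reported efficacy of the therapy is 98"%. The expectation of no failures returns as 100% SVR in Sections 4.2.1, 10.2, 10.4.2 and 10.5. Section 10.4.2 attaches a consequence: "Any failure of therapy will be considered significant and will result in the halting of further enrollment". Section 10.5 likewise treats one failure as a significant departure from expectation, and Section 8.6 calls an emergency DSMB meeting after any treatment failure.

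**The concern.** Two zeros stand in one sentence, joined as premise and conclusion. The premise, no first-line failures, conflicts with the 2% and 98% printed on either side of it. The conclusion, no chronic infection, rests on that premise, and the rescue figures that might otherwise support it are both qualified.

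This section is the protocol's statement of the main added harm to recipients, so its figures should agree with each other. The zero also matches the 100% SVR expectation behind the reading of a single failure. If the true failure rate were 0%, no failure could occur, and one failure would always contradict the expectation. If it is 2%, one failure among a handful of patients is an ordinary chance event. The DSMB should know which of these it is looking at before a failure happens.

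**Working it through.** **Inputs.** Efficacy 98% (Sections 2.2.2, 2.4.1, 10.5). Failure 2% or less (2.4.1). Enrolment 20, about 70% infected and treated, and an estimated 7 treated (all 10.5). Rescue cure up to, or approaching, 100% (2.4.1).

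**The plan's figure.** Failure rate = 1 − 0.98 = 0.02, or 2%. The stated 0% is not reproduced; it would need 100% efficacy, which no section reports for Mavyret.

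**Number treated.** The plan supports three values:
- 0.70 × 20 = 14, from the percentage in Section 10.5. The wording there is garbled, and 70% may be meant as an upper figure.
- 7, the number that Section 10.5 goes on to use. This is 35% of 20 (7/20) and does not follow from 70%.
- 20, if everyone is treated from the time of transplant, as the acute-infection paragraph of Section 2.4.1 says. Section 2.1 and the Schedule of Events (Section 19) start treatment only after viremia is detected.

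**Chance of at least one failure.** With independent outcomes and failure rate p among n treated, expected failures = np and P(at least one) = 1 − (1 − p)^n.

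| n treated | Expected failures, p = 2% | P(at least one), p = 2% | P(at least one), p = 1% |
|---|---|---|---|
| 7 | 0.14 | 1 − 0.98^7 = 0.132 | 1 − 0.99^7 = 0.068 |
| 14 | 0.28 | 1 − 0.98^14 = 0.246 | 1 − 0.99^14 = 0.131 |
| 20 | 0.40 | 1 − 0.98^20 = 0.332 | 1 − 0.99^20 = 0.182 |

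The 1% column is an assumed value within the range of 2% or less.

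**Reading one failure.** P(at least one) is also the one-sided exact binomial p-value for observing a single failure. Every entry exceeds the 0.05 level in Section 10.4.1. The value falls below 0.05 only if the reference failure rate is well under the reported one and few are treated: at an assumed 0.5% and n = 7 it is 1 − 0.995^7 = 0.035.

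**Chronic infection.** Risk per treated patient = 0.02 × (1 − r), where r is the rescue cure rate. The plan gives no exact r, so the range is an assumption:
- r = 100%: 0%.
- r = 99%: 0.02 × 0.01 = 0.02%; among 14 treated, P(at least one) = 1 − 0.9998^14 = 0.3%.
- r = 95%: 0.02 × 0.05 = 0.10%; among 14 treated, 1 − 0.999^14 = 1.4%.

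**The case against.** The best defence is that 0% expresses an expectation, not an estimate, and that the plan gives some ground for optimism. The Protocol Summary credits Mavyret with a cure rate above 98%. Section 2.1 cites cure rates approaching 100% for chronic infection and a kidney study, also with donor-derived infection, in which every recipient was cured. Section 2.3 speaks of nearly 100%. Zero failures is also the most likely single result: 0.98^14 = 75.4% with 14 treated. All of this stands, so it would be wrong to say that 98% is the only efficacy figure in the plan. But the kidney study's regimen and size are not given, Section 2.4.1 does not cite it for the 0%, and a most likely count of zero is not a rate of zero.

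Some stronger readings are tempting, and the documents do not support them:
- A reader might infer that the section conceals the risk. It does not. It gives the 2% under its own label and goes on to rescue, chronic infection, cirrhosis, liver transplantation and death. Only a study-level probability is absent.
- A reader might infer that a best-case HCV risk of 0% is weighed against worst-case waiting-list mortality. The 26.7% is compared with the risk once treatment has failed, and the closing benefit-risk paragraph starts from 98%.
- A reader might treat both zeros as the same error. The 2% applies to first-line failure only; the plan's own condition for chronic infection brings the risk close to zero.
- A reader might take one in four as the answer. It needs 14 treated and exactly 2% failure, and it is not an upper bound.

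**Conclusion.** The point holds in a limited form. The first-line 0% is wrong on the plan's own figures: at the reported efficacy the expected rate is 2%, or somewhat less. The chronic 0% is overstated certainty rather than a large numerical error: about 0.02% to 0.10% per treated patient if rescue cures 95% to 99%, and exactly zero only if rescue never fails.

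At 98% efficacy the chance of at least one failure runs from 13% (7 treated) to 33% (20 treated), and at 1% failure from 7% to 18%. One failure is thus compatible with the reported efficacy and does not by itself show a statistically significant deviation. This assumes independent outcomes and that the efficacy reported in the Phase 3 trials carries over to lung recipients. It does not question the benefit-risk judgement or the enrolment halt, which may be kept as a precaution whatever its chance of being triggered.

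**What to change.** In Section 2.4.1, replace the sentence with wording to this effect: *about 2% or less of treated patients are expected to fail first-line treatment; chronic HCV after rescue is expected to be very unlikely but not impossible.*

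Reconcile Sections 2.1, 2.4.1, 10.5 and 19 on who is treated, when, and how many that makes. Then state the chance of at least one failure at 98% efficacy for that number, using the matching row of the table.

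In Sections 10.4.2 and 10.5, and in what the DSMB is told, add that a single failure is compatible with the reported 98% and is not by itself a statistically significant deviation. This point does not require any change to the halting rule.

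Check that the consent form and fact sheet, which are separate attachments and were not available here, do not repeat 0%.

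The cost is wording and a slightly less favourable stated risk. No endpoint, analysis, data collection or patient number changes.
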